## 5.6 Reproductive Information

### 5.6.1 Male Recipients

Male participants with female partners of childbearing potential are eligible to participate if they agree to one of the following during the protocol defined time frame in section 3.1:

- Be abstinent from penile-vaginal intercourse as their usual and preferred lifestyle (abstinent on a long term and persistent basis) and agree to remain abstinent.
- Use a male condom plus partner use of a contraceptive method with a failure rate of <1% per year as described above when having penile-vaginal intercourse with a woman of childbearing potential who is not currently pregnant. **NOTE:** Men with a pregnant or breastfeeding partner must agree to remain abstinent from penile-vaginal intercourse or use a male condom during each episode of penile penetration.

## 6. TOXICITIES AND DOSE DELAYS/DOSE MODIFICATIONS

The NCI Common Terminology Criteria for Adverse Events (CTCAE) v5 will be used to grade adverse events. Subjects enrolled in this study will be evaluated clinically and with standard laboratory tests before and at regular intervals during their participation in this study as specified in Study Calendar & Evaluations. Subjects will be evaluated for adverse events (all grades), serious adverse events, and adverse events requiring study drug interruption or discontinuation as specified in Study Calendar & Evaluations.

### 6.1 Dose Modifications for Lenvatinib

Management of some adverse reactions may require dose interruption, adjustment, or discontinuation of lenvatinib therapy. Upon resolution/improvement of an adverse reaction, treatment should be resumed at a reduced dose. Mild to moderate adverse reactions (eg, Grade 1 or 2) generally do not warrant interruption of lenvatinib or of the combination, unless intolerable to the patient despite optimal management. Severe and clinically relevant (eg, Grade 3 or 4) or intolerable adverse reactions that are considered to be possibly, probably or definitely related to lenvatinib, pembrolizumab or both require interruption of lenvatinib or the combination until improvement of the reaction to Grade 0-1 or baseline.

For lenvatinib-related toxicities, upon resolution/improvement of an adverse reaction to Grade 0-1 or baseline, treatment of lenvatinib should be resumed with one level dose reduction as outlined in the Table below. For patients deriving clinical benefit and persistent toxicities at the lowest (-3) dose of lenvatinib, please contact the sponsor-investigator and HCRN for consideration of lowering the dose further. No dose re-escalation is allowed unless discussion with the sponsor-investigator and HCRN occurs and approval is obtained.

Treatment should be discontinued in case of life-threatening reactions (e.g., Grade 4) with the exception of laboratory abnormality judged to be non-life-threatening, in which case they should be managed as severe reactions (e.g., Grade 3).

### 6.1.1 Dose Levels for Dose Reductions of Lenvatinib

Dose level	Dose of Lenvatinib
Starting Dose	20 mg
Dose level (-1)	14 mg
Dose level (-2)	10 mg
Dose level (-3)	8 mg

### 6.2 Dose Modifications for Pembrolizumab

AEs associated with pembrolizumab exposure, including coadministration with additional compounds, may represent an immunologic etiology. These immune-related AEs (irAEs) may occur shortly after the first dose or several months after the last dose of pembrolizumab/combination treatment and may affect more than one body system simultaneously. Therefore, early recognition and initiation of treatment is critical to reduce complications. Based on existing clinical study data, most irAEs were reversible and could be managed with interruptions of pembrolizumab/combination treatment, administration of corticosteroids and/or other supportive care. For suspected irAEs, ensure adequate evaluation to confirm etiology or exclude other causes. Additional procedures or tests such as bronchoscopy, endoscopy, skin biopsy may be included as part of the evaluation. Dose modification and toxicity management guidelines for irAEs associated with pembrolizumab are provided in Table 1.

**Table 1: Dose modification and toxicity management guidelines for immune-related AEs associated with pembrolizumab monotherapy and IO Combinations**

General instructions:				
irAEs	Toxicity Grade (CTCAE v5.0)	Action With Pembrolizumab	Corticosteroid and/or Other Therapies	Monitoring and Follow-up
Pneumonitis	Grade 2	Withhold	
 
Administer corticosteroids (initial dose of 1 to 2 mg/kg prednisone or equivalent) followed by taper
 
	
 
Monitor participants for signs and symptoms of pneumonitis
 
Evaluate participants with suspected pneumonitis with radiographic imaging and initiate corticosteroid treatment
 

	Recurrent Grade 2, Grade 3 or 4	Permanently discontinue	
 
Add prophylactic antibiotics for opportunistic infections
 
	
Diarrhea/Colitis	Grade 2 or 3	Withhold	
 
Administer corticosteroids (initial dose of 1 to 2 mg/kg prednisone or equivalent) followed by taper
 
	
 
Monitor participants for signs and symptoms of enterocolitis (ie, diarrhea, abdominal pain, blood or mucus in stool with or without fever) and of bowel perforation (ie, peritoneal signs and ileus)
 

	Recurrent Grade 3 or Grade 4	Permanently discontinue		

irAEs	Toxicity Grade (CTCAE v5.0)	Action With Pembrolizumab	Corticosteroid and/or Other Therapies	Monitoring and Follow-up
				
 
Participants with <math>\geq</math>Grade 2 diarrhea suspecting colitis should consider GI consultation and performing endoscopy to rule out colitis
 
Participants with diarrhea/colitis should be advised to drink liberal quantities of clear fluids. If sufficient oral fluid intake is not feasible, fluid and electrolytes should be substituted via IV infusion
 

AST or ALT Elevation or Increased Bilirubin	Grade 2 a	Withhold	
 
Administer corticosteroids (initial dose of 0.5 to 1 mg/kg prednisone or equivalent) followed by taper
 
	
 
Monitor with liver function tests (consider weekly or more frequently until liver enzyme value returned to baseline or is stable)
 

	Grade 3 b or 4 c	Permanently discontinue	
 
Administer corticosteroids (initial dose of 1 to 2 mg/kg prednisone or equivalent) followed by taper
 
	
T1DM or Hyperglycemia	New onset T1DM or Grade 3 or 4 hyperglycemia associated with evidence of $\beta$ -cell failure	Withhold d	
 
Initiate insulin replacement therapy for participants with T1DM
 
Administer antihyperglycemic in participants with hyperglycemia
 
	
 
Monitor participants for hyperglycemia or other signs and symptoms of diabetes
 

Hypophysitis	Grade 2	Withhold		

irAEs	Toxicity Grade (CTCAE v5.0)	Action With Pembrolizumab	Corticosteroid and/or Other Therapies	Monitoring and Follow-up
	Grade 3 or 4	Withhold or permanently discontinue d	
 
Administer corticosteroids and initiate hormonal replacements as clinically indicated
 
	
 
Monitor for signs and symptoms of hypophysitis (including hypopituitarism and adrenal insufficiency)
 

Hyperthyroidism	Grade 2	Continue	
 
Treat with nonselective beta-blockers (eg, propranolol) or thionamides as appropriate
 
	
 
Monitor for signs and symptoms of thyroid disorders
 

	Grade 3 or 4	Withhold or permanently discontinue d		
Hypothyroidism	Grade 2, 3 or 4	Continue	
 
Initiate thyroid replacement hormones (eg, levothyroxine or liothyronine) per standard of care
 
	
 
Monitor for signs and symptoms of thyroid disorders
 

Nephritis: grading according to increased creatinine or acute kidney injury	Grade 2	Withhold	
 
Administer corticosteroids (prednisone 1 to 2 mg/kg or equivalent) followed by taper
 
	
 
Monitor changes of renal function
 

	Grade 3 or 4	Permanently discontinue		
Neurological Toxicities	Grade 2	Withhold	
 
Based on severity of AE administer corticosteroids
 
	
 
Ensure adequate evaluation to confirm etiology and/or exclude other causes
 

	Grade 3 or 4	Permanently discontinue		
Myocarditis	Grade 1	Withhold	
 
Based on severity of AE administer corticosteroids
 
	
 
Ensure adequate evaluation to confirm etiology and/or exclude other causes
 

	Grade 2, 3 or 4	Permanently discontinue		

irAEs	Toxicity Grade (CTCAE v5.0)	Action With Pembrolizumab	Corticosteroid and/or Other Therapies	Monitoring and Follow-up
Exfoliative Dermatologic Conditions	Suspected SJS, TEN, or DRESS	Withhold	
 
Based on severity of AE administer corticosteroids
 
	
 
Ensure adequate evaluation to confirm etiology or exclude other causes
 

	Confirmed SJS, TEN, or DRESS	Permanently discontinue		
All Other irAEs	Persistent Grade 2	Withhold	
 
Based on severity of AE administer corticosteroids
 
	
 
Ensure adequate evaluation to confirm etiology or exclude other causes
 

	Grade 3	Withhold or discontinue based on the event e		
	Recurrent Grade 3 or Grade 4	Permanently discontinue		

AE(s)=adverse event(s); ALT= alanine aminotransferase; AST=aspartate aminotransferase; CTCAE=Common Terminology Criteria for Adverse Events; DRESS=Drug Rash with Eosinophilia and Systemic Symptom; GI=gastrointestinal; IO=immuno-oncology; ir=immune related; IV=intravenous; SJS=Stevens-Johnson Syndrome; T1DM=type 1 diabetes mellitus; TEN=Toxic Epidermal Necrolysis; ULN=upper limit of normal.

**Note: Non-irAE will be managed as appropriate, following clinical practice recommendations.**

- a AST/ALT: >3.0 to 5.0 x ULN if baseline normal; >3.0 to 5.0 x baseline, if baseline abnormal; bilirubin:>1.5 to 3.0 x ULN if baseline normal; >1.5 to 3.0 x baseline if baseline abnormal
- b AST/ALT: >5.0 to 20.0 x ULN, if baseline normal; >5.0 to 20.0 x baseline, if baseline abnormal; bilirubin:>3.0 to 10.0 x ULN if baseline normal; >3.0 to 10.0 x baseline if baseline abnormal
- c AST/ALT: >20.0 x ULN, if baseline normal; >20.0 x baseline, if baseline abnormal; bilirubin: >10.0 x ULN if baseline normal; >10.0 x baseline if baseline abnormal
- d The decision to withhold or permanently discontinue pembrolizumab is at the discretion of the investigator or treating physician. If control achieved or ≤ Grade 2, pembrolizumab may be resumed.
- e Events that require discontinuation include, but are not limited to: encephalitis and other clinically important irAEs (eg, vasculitis and sclerosing cholangitis).

### 6.3 Dose modification and toxicity management of infusion-reactions related to pembrolizumab

Pembrolizumab may cause severe or life-threatening infusion-reactions including severe hypersensitivity or anaphylaxis. Signs and symptoms usually develop during or shortly after drug infusion and generally resolve completely within 24 hours of completion of infusion. Dose modification and toxicity management guidelines on pembrolizumab associated infusion reactions are provided below.

**Table 2: Pembrolizumab Infusion Reaction Dose modification and Treatment Guidelines**

NCI CTCAE Grade	Treatment	Premedication at Subsequent Dosing
Grade 1 Mild reaction; infusion interruption not indicated; intervention not indicated	Increase monitoring of vital signs as medically indicated until the participant is deemed medically stable in the opinion of the investigator.	None
Grade 2 Requires therapy or infusion interruption but responds promptly to symptomatic treatment (e.g., antihistamines, NSAIDs, narcotics, IV fluids); prophylactic medications indicated for ≤24 hrs	
Stop Infusion.
 
Additional appropriate medical therapy may include but is not limited to:
 
IV fluids Antihistamines NSAIDs Acetaminophen Narcotics
 
Increase monitoring of vital signs as medically indicated until the participant is deemed medically stable in the opinion of the investigator.
 
If symptoms resolve within 1 hour of stopping drug infusion, the infusion may be restarted at 50% of the original infusion rate (e.g. from 100 mL/hr to 50 mL/hr). Otherwise dosing will be held until symptoms resolve and the participant should be premedicated for the next scheduled dose.
 
Participants who develop Grade 2 toxicity despite adequate premedication should be permanently discontinued from further study drug treatment
	Participant may be premedicated 1.5h (± 30 minutes) prior to infusion of Pembrolizumab with: Diphenhydramine 50 mg po (or equivalent dose of antihistamine). Acetaminophen 500-1000 mg po (or equivalent dose of analgesic).
Grades 3 or 4 Grade 3: Prolonged (i.e., not rapidly responsive to symptomatic medication and/or brief interruption of infusion); recurrence of symptoms following initial improvement; hospitalization indicated for other clinical sequelae (e.g., renal impairment, pulmonary infiltrates) Grade 4: Life-threatening; pressor or ventilatory support indicated	
Stop Infusion.
 
Additional appropriate medical therapy may include but is not limited to:
 
Epinephrine** IV fluids Antihistamines NSAIDs Acetaminophen Narcotics Oxygen Pressors Corticosteroids
 
Increase monitoring of vital signs as medically indicated until the participant is deemed medically stable in the opinion of the investigator.
	No subsequent dosing

	
Hospitalization may be indicated. **In cases of anaphylaxis, epinephrine should be used immediately. Participant is permanently discontinued from further study drug treatment.
	
Appropriate resuscitation equipment should be available at the bedside and a physician readily available during the period of drug administration.		

### 6.3 Dose Modifications for Overlapping Toxicities

Based on the known toxicity profiles of pembrolizumab and lenvatinib, certain treatment-related AEs are uniquely associated with one drug versus the other. For example, hypertension, arterial thrombotic events, proteinuria, and hemorrhagic events are known risks for lenvatinib treatment, while immune-related AEs are risks for pembrolizumab treatment. However, certain AEs, such as such as diarrhea, hypothyroidism, and liver enzyme elevation, may be initially considered attributable to either study drug. Therefore, evaluation of attribution is important for determining the study drug most likely related to the AE, or an alternative etiology, and subsequently proper clinical management. The following aspects should be considered:

#### 1. Timing of AE onset

Since lenvatinib is dosed daily and continuously due to a relatively short half-life (28 hours), and pembrolizumab is dosed Q3W due to a long half-life, lenvatinib can be interrupted to assess whether an AE improves/resolves with dechallenge (ie, interruption of treatment) based on the following two scenarios:

- If an AE is identified during a treatment cycle (ie, between 2 pembrolizumab doses), only lenvatinib dose interruption is needed.
- If an AE is identified at the beginning of a treatment cycle, lenvatinib can be interrupted and dosing of pembrolizumab should be held.

If the subject recovers from an AE in response to lenvatinib interruption (ie, positive dechallenge), the event is more likely to be related to lenvatinib. Otherwise, after excluding other alternative explanations, an immune-related AE should be considered.

#### 2. Severity of AE

If an AE is suspected to be treatment related and is severe/life threatening at the time of onset or is rapidly worsened, action including interrupting both drugs and initiating treatment with a corticosteroid (with exception of hypothyroidism, T1DM) and other supportive care should be taken promptly.

#### 3. Participants receiving the combination therapy (pembrolizumab + lenvatinib) must discontinue study therapy if any of the following occur:

- ALT or AST >5 X ULN for more than 2 weeks.

Pembrolizumab will have already been permanently discontinued per the Table above, but lenvatinib may be administered at a reduced dose by the time this criterion is met and must be permanently discontinued immediately.

- ALT or AST >3 X ULN and (TBL >2 X ULN or INR >1.5).

Although the Table above advises pembrolizumab to be withheld (interrupted), and advises lenvatinib to have no dose modification or a reduction, if this criterion is met, both drugs must be permanently discontinued immediately.

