### 3. ELIGIBILITY CRITERIA

#### 3.1 Inclusion Criteria

Subject must meet all of the following applicable inclusion criteria to participate in this study:

1. Written informed consent and HIPAA authorization for release of personal health information prior to registration. **NOTE:** HIPAA authorization may be included in the informed consent or obtained separately.
2. Age  $\geq$  18 years at the time of consent.
3. Eastern Cooperative Oncology Group (ECOG) performance status of 0 or 1 within 7 days prior to the date of registration.
4. The subject has histologically proven prostate cancer with radiologic evidence of metastases and at least one of the following:
  - Small-cell or NEPC morphology (determined by the enrolling center) on the basis of tissue sample.
  - Prostate adenocarcinoma with IHC staining for neuroendocrine markers (e.g., chromogranin and synaptophysin).
  - Presence of visceral metastases or high volume disease ( $> 4$  sites of metastases) with a PSA  $\leq 5$ .
  - Serum chromogranin A level  $\geq 5 \times$  upper limit of normal (ULN) and/or serum neuron specific enolase (NSE)  $\geq 2 \times$  ULN.
  - RB1 deletions or mutations noted on genomic testing
  - Trans-differentiated carcinoma or poorly-differentiated carcinoma
5. Subject has adequate organ function as defined in the table below; all screening labs to be obtained within 10 days prior to Cycle 1 Day 1.
  - Absolute neutrophil count (ANC)  $\geq 1500/\text{mm}^3$  without colony stimulating factor support
  - Platelets  $\geq 100,000/\text{mm}^3$
  - Hemoglobin  $\geq 9 \text{ g/dL}$ . Transfusions are allowed as needed.
  - Serum creatinine  $\leq 1.5 \times$  ULN or creatinine clearance (CrCl)  $\geq 30 \text{ mL/min}$ . For creatinine clearance estimation, the Cockcroft and Gault equation should be used.
  - Bilirubin  $\leq 1.5 \times$  the upper limit of normal (ULN) OR direct bilirubin  $\leq$  ULN for participants with total bilirubin levels  $> 1.5 \times$  ULN. For subjects with known Gilbert's disease, bilirubin  $\leq 3.0 \text{ mg/dL}$
  - Alanine aminotransferase (ALT) and aspartate aminotransferase (AST)  $\leq 2.5 \times$  ULN if no liver involvement, or  $\leq 5 \times$  ULN with liver involvement

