  - International normalized ratio (INR) OR prothrombin time (PT), Activated partial thromboplastin time (aPTT)  $\leq 1.5 \times$  ULN unless participant is receiving anticoagulant therapy as long as PT or aPTT is within therapeutic range of intended use of anticoagulants
  - Urine protein  $< 2+$  by urine dipstick

6. A male participant must agree to use of contraception during the treatment period and for at least 120 days after the last dose of study treatment and refrain from donating sperm during this period.
7. Projected life expectancy of at least 6 months as determined by treating physician.
8. As determined by the enrolling physician or protocol designee, ability of the subject to understand and comply with study procedures for the entire length of the study.

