9. Known active CNS metastases and/or carcinomatous meningitis. Participants with previously treated brain metastases may participate provided they are radiologically stable, i.e. without evidence of progression for at least 4 weeks by repeat imaging (note that the repeat imaging should be performed during study screening), clinically stable and without requirement of steroid treatment for at least 14 days prior to first dose of study treatment.
10. Received a live vaccine or live-attenuated vaccine within 30 days prior to the first dose of study drug. Administration of killed viruses are allowed. All COVID-19 vaccines are permitted at any time before or during the study.
11. Significant cardiovascular impairment: history of congestive heart failure greater than New York Heart Association (NYHA) Class II, unstable angina, myocardial infarction or stroke within 6 months of the first dose of study drug, or cardiac arrhythmia requiring medical treatment at Screening.
12. Bleeding or thrombotic disorders or subjects at risk for severe hemorrhage. The degree of tumor invasion/infiltration of major blood vessels (e.g. carotid artery) should be considered because of the potential risk of severe hemorrhage associated with tumor shrinkage/necrosis following lenvatinib therapy.
13. Subjects having  $> 1+$  proteinuria on urine dipstick testing unless a 24-hour urine collection for quantitative assessment indicates that the urine protein is  $< 1$  g/24 hours.
14. Diagnosis of immunodeficiency or is receiving chronic systemic steroid therapy (in dosing exceeding 10 mg daily of prednisone equivalent) or any other form of immunosuppressive therapy within 7 days prior to the first dose of study drug.
15. Severe hypersensitivity ( $\geq$  Grade 3) to pembrolizumab and/or any of its excipients.
16. Severe hypersensitivity ( $\geq$  Grade 3) to lenvatinib and/or any of its excipients.
17. Active autoimmune disease that has required systemic treatment in the past 2 years (i.e. with use of disease modifying agents, corticosteroids or immunosuppressive drugs). Replacement therapy (eg., thyroxine, insulin, or physiologic corticosteroid replacement therapy for adrenal or pituitary insufficiency, etc.) is not considered a form of systemic treatment. Replacement steroids for adrenal insufficiency or daily dose equivalent of 10 mg prednisone are allowed.

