## Key to Footnotes

1: Medical History; other data to obtain during this assessment includes a smoking history questionnaire and trial awareness question. In addition, prior anti-cancer treatment should be documented including medications (chemotherapy, checkpoint inhibitors, etc) radiation or surgery. Prior genomic sequencing and PD-L1 results are required if available. Diagnosis and staging to include pathology report and imaging reports.

2: Vital signs to include temperature, pulse, respirations, blood pressure, weight, and height (screening only) and ECOG performance status. Blood pressure should be monitored after 1 week of treatment with lenvatinib (around C1D7), then every 2 weeks for the first 2 months (C2D1 at clinic visit and C2D14) and Day 1 of every cycle thereafter while on treatment. If a subject develops systolic BP  $\geq$  140 mmHg or diastolic BP  $\geq$  90 mmHg active management is indicated. Monitoring may be done locally by clinic visit, at home BP monitoring or similar. Subjects will be asked to maintain a record of BP readings and communicate results to research staff at timepoints as outlined above. ECG to be performed at screening then as clinically indicated during study treatment per investigator discretion.

3: CBC with differential and platelet to include: WBC, ANC, Hgb, Hct, PLT. CMP to include sodium, potassium, chloride, creatinine, blood urea nitrogen; calcium, albumin, and liver function tests (LFTs). LFTs to include AST, ALT, total bilirubin, and alkaline phosphatase; LFTs will be monitored every 2 weeks for 2 months (C1D14, C2D1, C2D14, C3D1). PT/INR and PTT should be obtained at screening then at site investigator discretion. Thyroid Function testing should be performed at screening then every 4 cycles (12 weeks). TSH should be obtained. T4 and T3 including free versus total testing is at the discretion of the site investigator. Urine protein should be obtained at screening then every 3 cycles (9 weeks). If urine dipstick  $\geq$  2+ is detected, dose interruptions, adjustments, or discontinuation may be necessary.

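### Minor: Section 3.1 can admit a patient with liver involvement whose entry values already meet the Section 6.3 liver rule for permanently stopping both drugs

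*Combined protocol and SAP*

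**What the plan says.** **Stop rule.** Item 3 of the second of the two sections numbered 6.3 lists when a participant on the combination has to come off study therapy. Its second criterion is "ALT or AST >3 X ULN and (TBL >2 X ULN or INR >1.5"). The text below it says that this overrides the milder action in the Table and that both drugs stop permanently and at once. It states no condition on baseline, direct bilirubin, Gilbert's disease or anticoagulant use.

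**Entry limits (Section 3.1, item 5).**
- ALT and AST: up to 2.5 x ULN, or up to 5 x "ULN with liver involvement".
- Bilirubin: total up to 1.5 x ULN, or direct bilirubin no higher than "ULN for participants with total bilirubin levels" above 1.5 x ULN. No upper limit on total bilirubin is given in that case.
- "For subjects with known Gilbert's disease, bilirubin" may be up to 3.0 mg/dL.
- Coagulation: "International normalized ratio (INR) OR prothrombin time (PT), Activated partial thromboplastin time (aPTT") up to 1.5 x ULN, "unless participant is receiving anticoagulant therapy as long as PT or aPTT is within therapeutic range of intended use of anticoagulants".

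**Monitoring (Section 7, footnote 3).** "LFTs to include AST, ALT, total bilirubin, and alkaline phosphatase"; direct bilirubin is not listed. Liver tests fall at C1D14, C2D1, C2D14 and C3D1, then with the Day 1 metabolic panel. After screening, INR is measured only if the site chooses.

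**The concern.** The entry criteria and the stop rule were set on different terms. Section 3.1 uses allowances for liver involvement, unconjugated bilirubin and anticoagulation; item 3 uses absolute values. Where the two ranges overlap, a patient can be enrolled correctly and then be taken off both drugs on values that have not moved.

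For that patient the loss is irreversible. At C1D14 he would have had one pembrolizumab infusion out of a possible 35 cycles, and Section 1.2 says there is no standard of care after platinum and etoposide. The fixed imaging schedule in footnote 5 also ends when study therapy ends, after which scans are at the site's discretion. Sites might also act differently on the same values, some following the letter of item 3 and others judging that nothing has changed.

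**Working it through.** The plan gives no figure on this point, and none of the two-stage design figures enters it. The check sets the entry limits against the stop rule, limb by limb.

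**Inputs.** Entry limits: Section 3.1, item 5. Stop rule S: (ALT/AST > 3 x ULN) and (TBL > 2 x ULN or INR > 1.5), Section 6.3 item 3. Laboratory ULNs are not in the documents. Assumed ranges: bilirubin ULN 1.0 to 1.5 mg/dL, INR ULN 1.0 to 1.2.

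**1. ALT/AST limb.**
- Liver involvement: entry up to 5, stop above 3. The overlap is above 3 and up to 5 x ULN.
- No liver involvement: entry up to 2.5, which is below 3. There is no overlap.

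**2. Bilirubin limb.**
- Ordinary limit: 1.5 x ULN is below 2 x ULN. No overlap.
- Direct bilirubin at or below ULN: total bilirubin is uncapped, so any value above 2 x ULN overlaps.
- Gilbert's disease: the entry limit in multiples of ULN is 3.0 / ULN.

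| Assumed bilirubin ULN (mg/dL) | 3.0 / ULN | Above 2 x ULN? |
|---|---|---|
| 1.0 | 3.0 | yes |
| 1.2 | 2.5 | yes |
| 1.3 | 2.31 | yes |
| 1.5 | 2.0 | no (equal) |

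**3. INR limb.**
- On a therapeutic anticoagulant the entry limit is waived, so an INR above 1.5 is admissible.
- Not on an anticoagulant: the entry limit is 1.5 x ULN, the stop value is an absolute 1.5. For an assumed INR ULN of 1.0, 1.1 and 1.2, the entry limit is 1.5, 1.65 and 1.8. Above a ULN of 1.0 there is a small overlap caused only by the two scales.

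**4. Patients at unchanged baseline.**
- Liver involvement, AST 4 x ULN, total bilirubin 2.1 x ULN, direct bilirubin at or below ULN: meets the hepatic and coagulation entry limits (INR normal) and meets S.
- Liver involvement, AST 4 x ULN, INR 2.5 on a therapeutic anticoagulant: likewise.

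A grid over ALT/AST 0.5 to 6 x ULN, TBL 0.2 to 4 x ULN and INR 0.8 to 3.5 agrees. There is no overlapping point without liver involvement. With liver involvement and no exception, there is none at an INR ULN of 1.0.

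**5. Same exceptions, no liver involvement.** If the second limb is already met at entry, S reduces to ALT/AST > 3 x ULN. From the entry limit, 3 / 2.5 = 1.20, so a rise of more than 20% is needed. This is a sensitive trigger, but not a zero-change one.

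**6. Does another provision remove the overlap?** Table 1 footnotes a to c grade liver tests against an abnormal baseline, but item 3 expressly takes precedence over the Table. The C1D14 panel reports total bilirubin only, so it cannot show that the raised value is the unconjugated pattern that Section 3.1 accepted.

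**The case against.** **Context implies a new event.** Item 3 sits under overlapping toxicities, where the section asks for attribution to a drug or another cause. Its lead-in speaks of values that occur, and Section 11.1.1 defines an adverse event by a change in intensity. Stable Gilbert's bilirubin is not naturally such an event. This is a fair reading, and it rules out saying that Section 6.3 ignores attribution. But no baseline condition is written, and the instruction is mandatory and immediate, so the ambiguity stands.

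**Rarity.** This stands. The zero-change case needs liver involvement, entry ALT/AST above 3 x ULN and a bilirubin or INR value above the stop level, in at most 50 patients. The INR route is narrower still: testing is discretionary, and Section 3.2 excludes arrhythmia needing treatment (item 11) and "Bleeding or thrombotic disorders or subjects at risk for severe hemorrhage" (item 12).

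**Copying every entry allowance into the stop rule would be unsafe.** This also stands. A reader might infer that item 3 should simply mirror Section 3.1. The 3.0 mg/dL Gilbert's limit is a screening allowance; used on treatment, it would disregard a newly raised direct bilirubin. A blanket INR exception would apply at any ALT level. Table 1 is a weak backstop here: from an entry ALT of 4 x ULN, withholding starts above 3 x 4 = 12 x ULN.

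**Section 11.1.7.** A reader might see a contradiction in its similar hepatic pattern, which calls for possible further evaluation. It is a reporting trigger and does not conflict with a stop rule.

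**Conclusion.** The overlap is in the text and follows by comparing limits; it rests on no frequency assumption. It is confined, at zero change, to patients with liver involvement and entry ALT/AST above 3 and up to 5 x ULN who also have unconjugated hyperbilirubinaemia, Gilbert's disease or an anticoagulant-raised INR. The Gilbert's route assumes a bilirubin ULN below 1.5 mg/dL. The small INR-scale overlap without an anticoagulant assumes an INR ULN above 1.0.

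The point is minor. A reader might infer that the protocol sets out to enrol these patients as a group, or that the primary endpoint is biased. The documents support neither: Section 3.1 grants each allowance separately, and nothing allows the number affected or any effect on 6-month rPFS to be derived. No sample size or decision boundary changes. What remains is a possible irreversible loss of treatment without a drug-caused change, which a short amendment can prevent.

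**What to change.** 1. **Section 3.1:** add that a patient whose screening values already meet the second criterion of Section 6.3 item 3 is not eligible, unless total bilirubin above 2 x ULN is the only second limb met and direct bilirubin is at or below ULN.
2. **Section 6.3 item 3, second criterion:** disregard total bilirubin only while direct bilirubin on the same sample is at or below ULN. Apply this to Gilbert's disease too, with no separate 3.0 mg/dL allowance. In Section 7 footnote 3, add a reflex direct bilirubin whenever total bilirubin exceeds 2 x ULN.
3. **INR:** use one scale. Set Section 3.1 to INR of 1.5 or less for patients not on an anticoagulant.
4. **Cross-reference:** item 3 attributes lenvatinib advice to the Table, but Table 1 gives actions for pembrolizumab only. Point to Section 6.1, where the lenvatinib advice is, and keep the sentence.

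Whether to allow an on-treatment exception for an anticoagulated INR is a clinical safety judgement for the sponsor. The first criterion, Table 1 and the reporting rule in Section 11.1.7 stay as they are.

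With these changes, a patient admitted under the amended Section 3.1 cannot meet the second criterion at unchanged values: either he was not eligible, or his bilirubin is not counted.

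**Cost:** an amendment to three places plus the cross-reference, a very small loss of eligible patients, a slightly narrower bilirubin limb, and an occasional assay on a sample already drawn. No added visits.
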